### 8.1 Clinical Study Protocol C-SY 00093

A multicenter clinical study was conducted at four sites in Israel in 2017. Sixty-Six subjects were enrolled (40 Men (61%) and 26 Women (39%), BMI <40), of which three failed to ingest the capsule, including one subject with a known swallowing disorder which was not disclosed to the study team during screening. Forty-Three had polyp(s) (65%) as indicated by their prior recent colonoscopy reports and the other 23 were considered as average risk population without any prior information about their colon.

All study procedures were completed and feedback from most subjects was positive and reassuring that the procedure was well-tolerated.

All capsules (except one) were collected and retrieved for QA inspection. They were all found to be intact and hermetically sealed.

The total transit time (TTT) is measured in hours between capsule ingestion to excretion. The TTT is the sum of 3 distinct sections:

- Time until reaching the caecum
- Time capsule dwells in the caecum
- Time of colon passage until excretion

The following table is the summary of all 63 cases in whom the study was completed (3 did not ingest). The standard deviation (STD) is quite high due to the considerable variability in bowel motility.

	Total Transit Time	Time to Caecum	Time in Caecum	Passage in colon
Average (hours)	52.3	15.9	16.8	16.5
STD	32.9	13.7	18.8	12.1

Table 2: Average transit time of the 3 sections of the GI tract and the standard deviation in each one.

There were no cases of C-Scan capsule retention (medical definition of Capsule retention is when TTT is longer than 300 hours – about 13 days).

The C-Scan is designed to operate continuously for 100 hours. There was one case in which the capsule was retained for 100-200 hours and then removed during the follow-up colonoscopy procedure

	Document Title	Clinical Investigational Plan For Study CL-SY-02-0096		
	Document No.	DOC001593	Revision	03

and in another case it was initiated by the sponsor since the batteries in the capsule were already depleted and no additional benefit was expected from the procedure. In two other cases, drugs (*Picolax*) were used to expedite the expulsion of faulty capsules (that stopped working). In all four cases the total time was less than 200 hours. In one case the capsule was not retrieved by the patient at the end of the procedure and, probably lost in the sewage system. Abdominal X-ray on the following day confirmed that the capsule was expelled with no residual in the GI tract images. All cases were completed uneventfully.

Several adverse events were reported including one case of irritating sensation in the esophagus that lingered for hours after capsule ingestion, skin irritation (under the stickers), soft stool, abdominal pain, headache, radiation level (body dose) was significantly higher than the typical dose of 50 uSV and four cases in which the transit time was longer than 120 hours. Three SAE events occurred including one hemorrhage/hematoma seen on abdominal wall, one post-colonoscopy bleeding and one post-colonoscopy abdominal pain. All SAE were non-related to device or C-Scan procedure and resolved without medical intervention. Several technical malfunctions occurred during the study, none of which resulted in harm to the subject but did not provide any data regarding the performance of the C-Scan system. During the study, updates were made to the system software to continue to optimize the algorithm and the ability to collect additional physiological data.

This study demonstrated that the C-Scan procedure was safe as no device- related serious adverse event occurred in any C-Scan clinical trial and the procedure was well-tolerated by the participating volunteers. The primary end point of safety for the C-Scan system was demonstrated. The primary end point for performance in terms of Positive Percent Agreement resulted in 44% capsule vs 37% for FIT. The protocol target was set at 55%, hence superiority was demonstrated with a lower than expected result. The result of Negative Percent Agreement was 89% vs. a set target of 75%, hence target surpassed the expected result.

## 8.2 Laboratory Tests

Rigorous laboratory tests have been performed on the Check-Cap Ltd. C-Scan System

### 8.2.1 Image Reconstruction

Based on the laboratory tests performed with the current version of our imaging capsule, polyps of 6 mm and larger should be visible and 10 mm polyps and larger are expected to be detected at high sensitivity. To further enhance the visibility of 6 mm - 9 mm polyps, a new design of the collimator was successfully tested in a future version of our imaging capsule, which enables 2.5 times the number of photons to be detected on the detectors, allowing the implementation of image enhancement algorithm, which is expected to improve the imaging performance.

### 8.2.2 Polyp Detection

Laboratory tests were carried out to estimate the capsule's ability to detect polyps in phantoms and demonstrate sensitivity and specificity of such detection ("*Polyp Detection Analysis*" in the *Investigator's Brochure (IB)*). Fusion of CMT and XRF data contributed to noise reduction and enabled to demonstrate 100% true positive and 0% false positive.

### 8.2.3 Biocompatibility

Successful Biocompatibility test performed on Nov/2015 (NAMSA) stated there were no deviations to the provisions of the FDA Good Laboratory Practice (GLP) Regulations (21 CFR, Part 58) noted during the course of the study.

	Document Title	Clinical Investigational Plan For Study CL-SY-02-0096		
	Document No.	DOC001593	Revision	03

#### **8.2.4 Animal Studies:**

Raw data from an animal colon ("Animal Testing and Tissue Equivalent Phantom Image Reconstruction" in the IB) showing a decrease in X-ray fluorescence (XRF), photon signals and an increase in Compton backscattering, or CMT, signals corresponding to the position of a polyp that was detected when our imaging capsule passed over the polyp.

CONFIDENTIAL

The information contained in this document is confidential and the sole property of "Check-Cap"  
Any reproduction in part or whole without the written permission of "Check-Cap" is prohibited

	Document Title	Clinical Investigational Plan For Study CL-SY-02-0096		
	Document No.	DOC001593	Revision	03

## 9 INVESTIGATIONAL DEVICE

### 9.1 Device Description

The C-Scan technology (Figure 1) is designed to provide structural information of the human colon without the need for fasting and prior bowel cleansing, eliminating the need to sedate subject and obviating the requirement for the insufflation of colon.

The system modality generates structural information on the colon, and is intended as a preliminary assessment of the colon which could assist in the detection of pre-cancerous polyps.

#### 9.1.1 C-Scan System Components

Figure 1 : Components of the C-Scan System

	Document Title	Clinical Investigational Plan For Study CL-SY-02-0096		
	Document No.	DOC001593	Revision	03

- C-Scan® Cap: Ingestible capsule (C-Scan Cap) enabling intra-colon feature visualization, based on a radioactive source and an array of detectors.
- C-Scan® Track: External Capsule Positioning System (CPS) incorporated into the C-Scan Track attached to the subject's back, communicates with the C-Scan Cap, and stores all procedure data.
- C-Scan® View: A PC based Workstation (C-Scan View) that enables procedure data loading from the C-Scan Track, managing of subject information, 2D and 3D colon imaging, reports generation and printouts and storage/reload of procedure data to and from a CD. An Algorithm uses these subsystems to estimate the C-Scan Cap position (using electromagnetic signals generated within the C-Scan Cap and the C-Scan Track), identifies C-Scan Cap movements in the colon and correspondingly initiates C-Scan Cap scans using a dedicated Scan Control Algorithm (SCA)

At the beginning of C-Scan procedure, the subject is connected to the C-Scan Tracker and asked to ingest the C-Scan Capsule. In order to increase the contrast of the colon's walls and to differentiate them from their content, it is essential to increase the stool's contrast by ingesting radio-opaque material. It is a standard procedure using approved Iodine based liquids, contrast agents such as (Telebrix or Gastrografine) at the discretion of the hospital similar to the preparation to abdominal CT. After ingestion, the subject can go about his or her normal daily routine. The capsule travels painlessly through the gastrointestinal tract, seeking polyps.

During the passage of the capsule in the gastrointestinal tract, it transmits information to the C-Scan Tracker (recorder) attached to the patient's back. In order to collect data about the instantaneous localization of the capsule traveling in the colon, sensors are embedded in the recorder.

### 9.1.2 Radio Frequency (RF) Wrist Watch

The watch is an optional monitoring tool to optimize data interpretation during the clinical study and is not an integral part of the C-Scan system, as in Figure 2.

Figure 2: RF Wrist Watch

A commercial wrist watch (product of Texas Instruments) is supplied with the C-Scan system for use by the subject during the procedure. The watch incorporates a passive RF receiver which is tuned to 'listen' and display the information transmitted from the capsule to the Track. The added information is valuable for the subject to follow the progress of the capsule and to better understand messages from the system.

	Document Title	Clinical Investigational Plan For Study CL-SY-02-0096		
	Document No.	DOC001593	Revision	03

## 10 STUDY OBJECTIVES

### 10.1 Primary Objectives

To evaluate the safety of the Check-Cap C-Scan System.

### 10.2 Secondary Objectives

- To evaluate subject's compliance
- To evaluate subject's satisfaction
- To collect data to improve the product's algorithm

### 10.3 Primary Safety Outcome Measure

The safety of the Check-Cap System will be evaluated by the incidence of device or procedure related Serious Adverse Events (SAE), as adjudicated by the Independent Physician Adjudicator.

### 10.4 Secondary Outcome Measures

- Subject compliance will be assessed by
  - Non-compliance rate throughout the study via diary completion by the subject Specific questionnaire completed by remote subject monitoring (via telephone)
- Subject satisfaction will be established by:
  - Designated questionnaire that focuses on patient's impressions regarding tolerance and potential safety concerns. Acceptance criteria was defined as average score >3.5 (1- low satisfaction to 5- high satisfaction), which represent high satisfaction with the safety and tolerance of the C-scan system.
  - Comparing patient's satisfaction with colonoscopy procedure.
- Collecting procedure related data:
  - Technical performance in normal daily routine.
  - Segmental transit time.
  - Procedure duration.
  - Bowel movements.
  - Agreement between C-Scan and colonoscopy with respect to the presence/absence of colonic polyp(s) [Note: C-scan data not to be used for clinical decision making in the care of patients, for this clinical study].
  - Inter-observer variability in the detection of significant clinical findings on a 'per patient' decision
- Battery life Assessment
  - Assessing adequate power supply for complete scan of the colon: length of capsule operation lifetime with respect to the lifetime specification of 100 +/- 10% hours.
- Device performance
  - Assessing colon model by the physician reviewers as presented on C-Scan View (e.g., normal, partial, right side missing, etc.).
  - Collecting data to improve the product's algorithm.

	Document Title	Clinical Investigational Plan For Study CL-SY-02-0096		
	Document No.	DOC001593	Revision	03

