### **13.6.2 Capsule Progress Days: Contrast Ingestion, Laxatives and Non-Soluble Fiber**

One the days in which the capsule is progressing within the subject, the subject is required to ingest contrast media (GE Omnipaque 350, FDA approved under NDA 018956) as well as non-soluble fiber supplements. The subject will be required to ingest daily dose (3 X 15 ml) of contrast media, to be consumed three times per day as well a non-soluble fiber 3x/day with normal diet.

The subject will be provided with Laxadin (5 mg tablets) to be ingested according to the doctor recommendation, on an as needed basis. In routine procedures, subjects might be instructed to take 2 X 5 mg tablets 48-72 hours after ingestions (unless the capsule was already excreted).

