### **13.6.3 Subject Diary**

All subjects will be required to keep a log ('Subject's Diary') during procedure documenting general activities, contrast media intake, fibers intake, and food consumption, bowel movement, and system visual/auditory indicators.

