### **13.7 Follow Up 2: Capsule excretion and collection**

#### **13.7.1 Capsule Return**

Capsule procedure is completed upon capsule excretion or system auditory indication of 'End of Procedure'. Subjects will be instructed to inform the study coordinator or designee upon capsule excretion.

The subjects will be provided with a dedicated capsule collection kit, to assist the subjects in collecting the capsule. Subjects will be instructed to retrieve the capsule upon excretion. Return packaging and instructions will be provided. The subject will return with the Kit the diary, the questionnaire and all unused materials.

In case of doubt regarding capsule excretion, and per physician discretion, subjects may be referred to abdominal X-Ray to confirm capsule excretion.

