## **19 DELIVERY, STORAGE AND DISPOSITION**

The C-Scan capsule and accessory kit will be shipped to the investigative site in advance of the procedure. Based upon the cadence of scheduled procedures, the site may be provided several units at a time to have inventory on hand.

All device and accessories must be tracked within the device accountability log and stored in a secure location available to only authorized study personnel. C-Scan should be kept in a dry location at room temperature.

At the end of the C-Scan procedure, a representative of the sponsor will collect the Kit, document and all unused material directly from the subject. C-Scan units returned from the subject will be shipped back to the sponsor.

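### Compliance is measured only by subject self-report (diary and telephone questionnaire); the unused materials that subjects return are not used to check contrast and fibre intake

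*Combined protocol and SAP*

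**What the plan says.** - **Objective.** Section 10.2 lists "To evaluate subject's compliance" among three secondary objectives.
- **Measure.** Section 10.4 names two sources: "Non-compliance rate throughout the study via diary completion by the subject", and a specific questionnaire completed through telephone monitoring. It gives no numerator, denominator or threshold, and does not say whether the rate is scored on the diary being filled in or on the intake it records.
- **Diary content.** Section 13.6.3 has the subject keep a log "documenting general activities, contrast media intake, fibers intake, and food consumption, bowel movement, and system visual/auditory indicators".
- **Home regimen.** Section 13.6.2 states: "The subject will be required to ingest daily dose (3 X 15 ml) of contrast media, to be consumed three times per day". Non-soluble fibre is also taken three times a day. Both apply on the days when the capsule is still progressing.
- **Returns.** Section 13.7.1 states: "The subject will return with the Kit the diary, the questionnaire and all unused materials". Section 19 says that at the end of the procedure "a representative of the sponsor will collect the Kit, document and all unused material directly from the subject". The accountability log in Section 19 covers the device and accessories; contrast and fibre are not mentioned.

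**The concern.** Contrast and fibre are taken at home, apart from what is swallowed with the capsule under observation (Section 13.5.1). What is known about home intake is what the subject writes down or tells staff, who telephone at least twice a day. Subjects in that position tend to report what is expected of them, so the compliance figure is likely to be too favourable. The plan retrieves material that could serve as a check and assigns it no purpose.

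Two other parts of the plan lean on the same information. Sections 7.2 and 9.1.1 treat raised stool contrast as necessary for imaging, so unverified intake weakens any attempt to attribute a poor colon model to the device or to missed contrast. Section 14.1.3 removes cases from the statistical analysis for noncompliance and gives no criterion for it.

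**Working it through.** The plan states no compliance rate or target, so there is no figure to reproduce. The checks are whether a count of returned material would be informative, and how far a diary-based figure could drift.

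**1. Expected doses.** Inputs: three 15 ml doses of contrast per day (Section 13.6.2); total transit in the earlier study, mean 52.3 h and SD 32.9 h (Section 8.1). It is assumed that transit here resembles that study and that doses accrue evenly.

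Doses required = transit hours / 24 × 3; one dose as a share = 1 / doses required.

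| Transit | Doses required | One dose as share |
|---|---|---|
| 52.3 − 32.9 = 19.4 h | 2.4 | 41% |
| 52.3 h (mean) | 6.5 (98 ml) | 15% |
| 52.3 + 32.9 = 85.2 h | 10.7 | 9% |
| 100 h | 12.5 (188 ml) | 8% |

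A count is therefore a usable check at average or long transit and a coarse one at short transit. At 19.4 h, a two-dose discrepancy is 2 / 2.4, or about 82% of the requirement.

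**2. Drift of the diary figure.** Let c be true compliance and f the share of non-compliers whose diary looks full. Both are assumptions; the documents give neither.

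Apparent compliance = c + (1 − c) × f.

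| c | f = 0 | 25% | 50% | 75% | 100% |
|---|---|---|---|---|---|
| 70% | 70% | 77.5% | 85% | 92.5% | 100% |
| 80% | 80% | 85% | 90% | 95% | 100% |
| 90% | 90% | 92.5% | 95% | 97.5% | 100% |

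**3. What this means at n = 45.** If 9 of 45 subjects under-take the contrast (assumed), true non-compliance is 20%, exact 95% CI 9.6% to 34.6%. The diary would show 0% only if all nine diaries concealed the shortfall (f = 100%). At f = 50% it would show 10%, and at f = 0 the correct 20%.

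**4. Is the check already in the plan?** Sections 10.4, 13.6.2 to 13.7.1, 14.1.4 and 19 were compared. None counts returned contrast or fibre, compares it with the diary, or uses it for the compliance outcome. The topics listed for the daily calls in Section 13.6.4 do not include doses taken.

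**The case against.** The strongest reply is that the diary is already an intake record. A reader might infer from Section 10.4 that a filled-in diary passes for a completed regimen. The documents do not support that: Section 13.6.3 requires contrast and fibre entries, so a complete diary can show missed doses. The telephone questionnaire is a second source, and its content is not in the documents, so it may ask about doses. This stands, and it limits the point to unverified self-report and an unstated scoring rule.

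Four further replies carry weight:

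- **Return of contrast is inferred.** Sections 13.7.1 and 19 speak of unused materials without naming contrast. Contrast is a main home consumable, so its return is plausible but not stated.
- **There is no fixed total of doses.** Section 13.6.2 sets a daily rate. The total varies with transit, and the denominator needs an end time that may itself come from the subject. Packaging is not described, so volumes may have to be measured instead of units counted.
- **The count has its own bias.** A discarded dose looks taken.
- **Compliance is wider than contrast and fibre.** Section 10.4 refers to the whole study, and the FIT strip photo and the returned capsule already give objective evidence on other elements.

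These replies tell against making the count the main compliance measure. They do not tell against adding it as a cross-check. It is also fair that this is an unpowered pilot with descriptive analysis and no acceptance threshold for compliance, so the stakes are modest.

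**Conclusion.** The point holds as a cheap improvement to a secondary outcome. Compliance rests only on what subjects report, that is likely to overstate intake, and the returned materials have no role.

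The size of any overstatement cannot be derived from the documents. With assumed true compliance of 70%, the diary figure could lie anywhere from 70% to 100%; with 90%, from 90% to 100%. The contrast of 0% with 20% is the extreme end of such a range and should not be read as an expected result.

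A reader might also conclude that the estimate is certainly biased, or that poor images cannot be separated from missed contrast at all. Neither follows: the bias depends on how accurately diaries are kept, and the diary gives imperfect information on intake, not none. The usefulness of a count assumes that unused contrast and fibre are among the returned materials and that transit resembles the earlier study.

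**What to change.** 1. Log the contrast and fibre dispensed and returned with each kit, and name both among the unused materials in Sections 13.7.1 and 19.
2. In Section 10.4, score contrast and fibre compliance on intake, as doses taken divided by doses required from ingestion to the end of required intake, and not on whether the diary was filled in.
3. Report the diary-based figure and the dispensed-minus-returned figure side by side, and list subjects in whom they differ by more than one dose.
4. Report the other elements (FIT, capsule return, diary completion) separately.
5. State the limits with the result: the count is an upper limit on intake, and it is coarse when transit is short.

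The cost is one dispensing and return line per kit and a few sentences of analysis wording. No visit, procedure, sample-size change or change to the regimen is needed.

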## 14 STATISTICAL ANALYSIS

### 14.1.1 Sample Size Considerations

This is a pilot safety study; therefore, sample size is not determined by power analysis. Up to 45 subjects will be recruited to the study.

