### 23.1 ATTACHMENT 1: SUBJECT'S SATISFACTION QUESTIONNAIRE

#### Subject Satisfaction Questionnaire

Please circle the most appropriate answer for each question according to the following scale:

1. Strongly disagree
2. Disagree
3. Neither agree or disagree
4. Agree
5. Strongly agree

Space is provided for comments.

Scale

1. I have not experienced any inconvenience during the C-Scan procedure. If 1 or 2 are given, please explain:	1 2 3 4 5
2. I have not experienced any pain during the C-Scan procedure. If 1 or 2 are given, please explain:	1 2 3 4 5
3. I did not need any analgesic or other pain medication during the C-Scan procedure. If 1 or 2 are given, please explain:	1 2 3 4 5
4. I have not experienced any inconvenience while ingesting the contrast media 3 times a day If 1 or 2 are given, please explain:	1 2 3 4 5
5. I Would recommend the C-Scan procedure for colonic screening If 1 or 2 are given, please explain:	1 2 3 4 5
6. The C-Scan procedure didn't affect my daily routine If 1 or 2 are given, please explain:	1 2 3 4 5
7. I have not experienced any inconvenience during capsule excursion If 4 or 5 are given, please specify:	1 2 3 4 5
8. Do you have any additional comments regarding the C-Scan procedure?	

CONFIDENTIAL

	Document Title	Clinical Investigational Plan For Study CL-SY-02-0096		
	Document No.	DOC001593	Revision	03

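### An average satisfaction score above 3.5 does not carry the meaning section 10.4 gives it, because it can be reached with uniformly poor answers on pain

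*Combined protocol and SAP*

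**What the plan says.** Among the secondary outcomes, section 10.4 gives the threshold and its interpretation together: "Acceptance criteria was defined as average score >3.5 (1- low satisfaction to 5- high satisfaction), which represent high satisfaction with the safety and tolerance". It does not say whether the average runs over items, over subjects or over both. It adds no minimum for any item, no minimum share of satisfied subjects and no confidence limit.

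The C-Scan questionnaire in Attachment 1 (section 23.1) has seven items rated from 1 (strongly disagree) to 5 (strongly agree), all worded so that agreement is favourable; an eighth is free text. Item 2 reads "I have not experienced any pain during the C-Scan procedure" and item 3 reads "I did not need any analgesic or other pain medication during the C-Scan procedure". The other five cover inconvenience during the procedure, contrast intake, willingness to recommend, daily routine and capsule excretion.

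Section 14.1.4 plans descriptive statistics only. For ordinal data it commits to mean, standard error, median, minimum and maximum, and leaves counts and percentages optional. Section 14.1.1 says: "Up to 45 subjects will be recruited to the study".

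**The concern.** The threshold is the only rule in the protocol labelled an acceptance criterion, and its interpretation is fixed in advance. Two features weaken the link between the two.

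First, an average lets good scores on some items offset bad scores on others, and satisfied subjects offset dissatisfied ones. The two items that bear most directly on physical tolerance are two of seven, so the other five can outweigh them. Second, on the form's own anchors 3.5 lies midway between the neutral answer (3) and *Agree* (4), so a result described as high satisfaction does not require even average agreement.

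At stake is a reported statement about safety and tolerance that the answers on pain and analgesic use might contradict.

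**Working it through.** The 3.5 threshold is set rather than derived, so there is no calculation in the plan to reproduce. The check asks which answer patterns pass.

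**Inputs**
- Pass mark: average above 3.5 (section 10.4).
- Seven rated items scored 1 to 5, with pain as item 2 and analgesic need as item 3 (Attachment 1).
- 45 subjects, the maximum (section 14.1.1).
- Assumptions: the questionnaire meant in section 10.4 is Attachment 1, and the average is over all items and subjects.

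**Pain item alone.** Every subject scores 1 on item 2 and 4 on the other six: (1 + 6×4)/7 = 25/7 = 3.57. Pass, with no top scores needed.

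**Pain and analgesic items together.** Every subject scores s on items 2 and 3, and the other five average x. The mean is (2s + 5x)/7, which exceeds 3.5 when x > (24.5 − 2s)/5.
- s = 1: x must exceed 22.5/5 = 4.5. With x = 5 the mean is 27/7 = 3.86 (pass); with x = 4 it is 22/7 = 3.14 (fail).
- s = 2: x must exceed 20.5/5 = 4.1. With x = 4 the mean is 24/7 = 3.43 (fail).

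**Dissatisfied subjects.** Of 45 subjects, m score 1 throughout and the rest average t. The total must exceed 3.5×45 = 157.5, so t > (157.5 − m)/(45 − m).
- m = 16 (36%): t must exceed 141.5/29 = 4.88. With t = 5 the mean is (16 + 145)/45 = 161/45 = 3.58 (pass).
- m = 17: even t = 5 gives (17 + 140)/45 = 157/45 = 3.49 (fail).
- m = 15 (a third): t must exceed 142.5/30 = 4.75.
- If the rest score 4, m = 7 gives (7 + 152)/45 = 3.53 (pass) and m = 8 gives (8 + 148)/45 = 3.47 (fail).

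**Other readings of the average.** If each item had to exceed 3.5, the pain patterns would fail, but the split with 16 at 1 and 29 at 5 would pass, because every item averages 3.58. If each subject had to exceed 3.5, the split would fail, but the pain patterns at 3.57 and 3.86 would pass. Each reading still lets one type of pattern through.

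**Item 7.** The form reads "I have not experienced any inconvenience during capsule excursion If 4 or 5 are given, please specify". The statement is favourable, but the request to explain is tied to the high scores, whereas items 1 to 6 tie it to 1 or 2. Some subjects may therefore answer it in reverse. Dropping the item does not change the conclusion: 1 on items 2 and 3 and 5 on the remaining four gives 22/6 = 3.67 (pass).

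**The case against.** The strongest reply is that these are corner cases. Subjects in pain and taking analgesics would rarely also report near-perfect convenience, and a dissatisfied third needs almost uniform top scores from everyone else. Any criterion based on a mean can be defeated this way. That largely stands for the two extreme patterns. It is weaker for the pain item alone, where plain agreement elsewhere suffices.

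Items 1, 4 and 7, on inconvenience during the procedure, with contrast and at excretion, can also be read as tolerance items. That stands, so items 2 and 3 are the most direct tolerance items, not the only ones.

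The planned minimum, median and standard error would reveal part of the picture. If each item is summarised, universal pain would show as an item mean of 1. But section 14.1.4 does not say that items are summarised separately, and no such summary alters the pass or its meaning. In the split with 16 at 1 and 29 at 5, the 23rd ordered value is 5, so the median would be 5 with a minimum of 1, and the size of the dissatisfied group would not be shown directly.

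A reader might infer that the rule could hide a safety problem or declare the device safe. The documents do not support that. Section 10.4 speaks of satisfaction with safety. Safety itself is judged by adjudicated device- or procedure-related serious adverse events (section 10.3). Abdominal pain and discomfort are recorded as adverse events (section 16.2), subjects are telephoned at least twice daily until excretion (section 13.1, Table 1), and scores of 1 or 2 on items 2 and 3 prompt an explanation.

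Nor is this the only outcome set against a figure: section 10.4 also assesses battery life against a specification of 100 hours ± 10%.

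**Conclusion.** The point holds in limited form. Passing the 3.5 average does not establish the safety-and-tolerance interpretation attached to it. On the natural reading, universal strong disagreement on the pain item is compatible with a pass at 3.57. The lowest score on both pain and analgesic need passes only when the other items average above 4.5. Up to 16 of 45 subjects at the lowest score throughout passes only when the rest average above about 4.88. It would be wrong to infer that universal pain and analgesic use, or a dissatisfied third, generally passes: with 4 in place of near-top scores these patterns give 3.14 and (15 + 30×4)/45 = 3.00.

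The conclusion assumes Attachment 1 is the questionnaire meant, seven equally weighted items and 45 subjects. It concerns a secondary, descriptive outcome in a pilot study whose size rests on no power analysis. The weakness is in what the rule is said to mean. It is worth correcting because that meaning is fixed before the data are seen and would shape what the trial may claim.

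**What to change.** In section 10.4:
- State that the average is taken over the seven rated items and all subjects.
- Treat a value above 3.5 as a summary of overall acceptability only, and remove safety and tolerance from its interpretation.
- Base any statement on tolerance on items 2 and 3, reported separately.

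In section 14.1.4, require the number and percentage of subjects scoring 1 or 2 on each item, in place of the present option.

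In Attachment 1, reconcile the prompt on item 7 with its wording before any average is computed.

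Applying the 3.5 threshold to items 2 and 3 separately is optional and partly a matter of preference. It would catch universal pain but not a dissatisfied third, since the split with 16 at 1 and 29 at 5 gives 3.58 on each item. The item counts would show it.

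The cost is wording, one more table from data already collected, and a somewhat less favourable claim.
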